
To assess efficacy of 250-mg mirikizumab Q8W and 125-mg mirikizumab Q8W as compared to secukinumab with respect to clinical response
	
At Week 52 and at various time points during the Maintenance Dosing Period:
 
 • Proportion of patients achieving PASI 90 • Proportion of patients achieving a DLQI total score of (0,1) with at least a 5-point improvement (reduction) from baseline in patients with a baseline DLQI total score ≥ 5 • Proportion of patients achieving DLQI (0,1) with DLQI baseline score >1

Evaluate the pharmacokinetics and pharmacokinetic/pharmacodynamic relationship of mirikizumab
	
 • Clearance and volume of distribution of mirikizumab • Relationship between mirikizumab exposure and efficacy (sPGA and PASI)

Exploratory
 
To evaluate the potential development of antimirikizumab antibodies and their potential relationship with efficacy, TEAEs, and mirikizumab exposure
	
At Week 16 and Week 52:
 
 • Relationship between TE-ADA and efficacy (sPGA and PASI) • Relationship between TE-ADA and TEAEs • Relationship between TE-ADA and mirikizumab pharmacokinetics

Protocol-Defined Objectives and Endpoints

Abbreviations: BSA = body surface area; DLQI = Dermatology Life Quality Index; MCS = mental component summary; NAPSI = Nail Psoriasis Severity Index; PASI = Psoriasis Area and Severity Index; PASI 75/90/100 = $\geq 75\%$ / $\geq 90\%$ / $\geq 100\%$ improvement in PASI from baseline; PatGA = Patient's Global Assessment of Psoriasis; PCS = physical component summary; PPASI = Palmoplantar Psoriasis Severity Index; PSS = Psoriasis Symptoms Scale; PSSI = Psoriasis Scalp Severity Index; Q8W = every 8 weeks; QIDS-SR16 = 16-item Quick Inventory of Depressive Symptomatology; SF-36 = Short Form 36-item Health Survey; sPGA = static Physician's Global Assessment; TE-ADA = treatment-emergent antidrug antibody; TEAE = treatment-emergent adverse event; WPAI PSO = Work Productivity Activity Impairment Questionnaire – Psoriasis.

- a All primary and major secondary endpoint analyses will utilize the multiplicity control technique called “graphical multiple testing procedure” to control the overall family-wise Type I error rate.

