6.3.1. Nonresponder Imputation

The nonresponder imputation (NRI) method can be justified based on the composite strategy (ICH E9R1) for handling intercurrent events. In this strategy patients are defined as responders only if they meet the clinical requirements for response at the predefined time AND they remain on the assigned study treatment. Failing either criteria by definition makes them nonresponders.

Analysis of binary categorical efficacy and health outcome variables will be assessed using an NRI method. Patients will be considered nonresponders for the NRI analysis if they do not meet the clinical response criteria or have missing clinical response data at the analysis time point. Randomized patients without at least 1 postbaseline observation will also be defined as nonresponders for the NRI analysis.

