6.14.6. Immunogenicity

An individual sample is potentially examined multiple times in a hierarchical procedure to produce a sample antidrug antibodies (ADA) assay result and potentially a sample neutralizing antidrug antibodies (NAb) assay result. A patient has treatment-emergent antidrug antibodies (TE-ADA) when ADAs are induced or boosted by exposure to study drug; that is, when at least 1 postbaseline ADA sample has a 4-fold increase in titer compared to baseline (if ADAs were present at baseline) or has a titer 2-fold greater than the minimum required dilution of 1:10 (if no ADAs were present at baseline).

Compound level safety standards will be followed in the analyses of immunogenicity. Listings of immunogenicity assessments will be provided-along with the summary of specified TEAEs by TE-ADA status. The summary of TE-ADA and NAb status will be produced for the 2 safety populations, where the postbaseline period for reporting is the same as described for AEs in Section 6.14.2. The subgroup analysis of efficacy by TE-ADA status (positive, negative) is described in the Section 6.15. Additional assessments of the relationship between immunogenicity and efficacy will be performed as part of the integrated analysis including other Phase 3 mirikizumab psoriasis trials.

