6.15. Subgroup Analyses

6.15.1. Efficacy Subgroup Analyses

Subgroup analyses will be conducted for the primary endpoints of Week 16 PASI 90 and sPGA (0,1) proportion in the ITT Population. Also, subgroup analysis for the Week 52 PASI 90 and sPGA (0,1) proportion in the ITT population will be performed. The subgroups to be analyzed are listed in [Table AMAJ.6.4](#) along with the demographic characteristics. Some additional subgroup analyses may be performed to meet regulatory requirements in specific countries. Additional subgroup analyses, which are not based on baseline/demographic characteristics in [Table AMAJ.6.4](#) are:

- concomitant topical steroid product use: yes, no.
- concomitant systemic corticosteroid use: yes, no
- treatment-emergent antimirikizumab antibody status: positive, negative

The analysis of additional subgroups will not require an amendment to the SAP. Missing outcome data will be imputed using NRI. Within each subgroup category the proportion of responders by treatment, treatment differences and 95% CIs will be displayed. Also, p-values using Fisher's exact test for treatment comparison will be provided. If the number of patients in any subgroup category is <10% of the total population, only summaries of the efficacy data will be provided (that is, no inferential testing). Forest plots will be generated to display the odds ratios and 95% CIs for the efficacy subgroup analyses.

A logistic regression model with treatment, subgroup, and the interaction of subgroup by treatment will be used. The subgroup-by-treatment interaction will be tested using the Firth correction (Firth 1993) at the significance level of 0.10.

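### The Week 52 comparison of response by anti-drug antibody status is open to follow-up-time bias; adding a Week 16 landmark analysis would be a cheap improvement

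*SAP*

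**What the plan says.** SAP Table AMAJ.4.1 lists "Relationship between TE-ADA and efficacy (sPGA and PASI" as an exploratory endpoint at Weeks 16 and 52. SAP 6.14.6 defines status over the whole postbaseline record. A patient with antibodies at baseline is positive "when at least 1 postbaseline ADA sample has a 4-fold increase in titer compared to baseline"; without them, one sample above a titre threshold is enough. The same section hands over the efficacy analysis: "The subgroup analysis of efficacy by TE-ADA status (positive, negative) is described in the Section 6.15".

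SAP 6.15.1 lists the subgroup as "treatment-emergent antimirikizumab antibody status: positive, negative", with no third category, and analyses it in the ITT population. It adds: "Missing outcome data will be imputed using NRI". Under SAP 6.3.1, nonresponders include patients who "have missing clinical response data at the analysis time point". That section goes on: "Randomized patients without at least 1 postbaseline observation will also be defined as nonresponders for the NRI analysis".

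For this analysis the SAP gives no landmark visit, no rule for patients without an evaluable postbaseline antibody sample, and no tabulation of discontinuation by antibody status.

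**The concern.** NRI suits the randomised comparisons, where the groups are fixed at baseline. Antibody status is not fixed at baseline. Under an ever-positive definition, the chance of being labelled positive grows with time under observation. A patient who stops in Week 8 has had little time to be found positive and is a Week 52 nonresponder by rule. Such patients tend to collect in the negative group and pull its response rate down, whether or not antibodies affect efficacy.

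What is at stake is how to read the one TE-ADA and efficacy analysis that this SAP specifies. A small difference, or none, between positive and negative patients could reflect who stayed in the study, and might be taken as evidence that antibodies do not matter.

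**Working it through.** The plan states no figure for this analysis, so there is none to reproduce. The one planning rate borrowed is the 75% Week 52 response in SAP 5.2. It underlies the stated 90% power against secukinumab at 65% with 444 per arm (two-sided 0.05), which recomputes as 90.3%.

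**Inputs**
- Response on treatment in antibody-negative patients, rn: 75% (SAP 5.2; its use as an on-treatment rate is an assumption).
- Response on treatment in antibody-positive patients, rp: 75%, 70% or 65%, for a true loss of 0, 5 or 10 points.
- Dropout before Week 52, d: 5%, 10%, 15% (assumed).
- TE-ADA rate in fully followed patients, a: 20% or 30% (assumed).
- Detection of positivity in dropouts relative to fully followed patients, k: 0.5, 0.8, 0.9 (assumed). If dropout and seroconversion are both spread evenly over 52 weeks and no later samples count, k = 0.5. If all seroconversion falls evenly within 16 weeks (mean Week 8), k = 1 - 8/52 = 0.85.

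**Formulas**
- Positives: (1-d)·a·rp / [(1-d)·a + d·a·k]
- Negatives: (1-d)·(1-a)·rn / [(1-d)·(1-a) + d·(1-a·k)]

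**Example**, no true effect, d = 10%, a = 20%, k = 0.5:
- Positives: 0.180 × 75% / (0.180 + 0.010) = 71.1%
- Negatives: 0.720 × 75% / (0.720 + 0.090) = 66.7%
- Spurious advantage of positives: +4.4 points

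**Positive minus negative, in points** (differences taken before rounding):

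| d, a | k | no loss | true -5 | true -10 |
|---|---|---|---|---|
| 5%, 20% | 0.5 | +2.3 | -2.6 | -7.5 |
| 10%, 20% | 0.5 | +4.4 | -0.4 | -5.1 |
| 15%, 30% | 0.5 | +7.2 | +2.6 | -2.0 |
| 5%, 20% | 0.8 | +0.9 | -3.9 | -8.7 |
| 10%, 20% | 0.8 | +1.7 | -2.9 | -7.5 |
| 15%, 30% | 0.8 | +2.8 | -1.6 | -6.0 |

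At k = 0.9 a true 5-point loss shows as -4.3, -3.7 and -2.9 in the same three settings. At k = 1 the bias is gone and only the NRI scaling (1-d) remains: -4.75, -4.5 and -4.25.

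**Outer bound.** If no dropout were ever found positive (k = 0) and 25% of fully followed patients were positive, a true 10-point loss would show as -5.1, -0.3 and +4.3 at 5%, 10% and 15% dropout.

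**Opposite direction.** Suppose antibodies cause a further 10% of positives to leave. The positive rate is then multiplied by 0.90. With k = 0.5 and a true on-treatment loss of 5 points:
- d = 5%, a = 20%: 61.4% vs 70.8%, or -9.4
- d = 10%, a = 20%: 59.7% vs 66.7%, or -7.0
- d = 15%, a = 30%: 57.9% vs 61.8%, or -3.9

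A true 10-point loss at d = 5%, a = 20% becomes 57.0% vs 70.8%, or -13.8.

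**Landmark version.** Status is fixed at Week 16 among patients still on treatment. With equal later dropout d' in both groups, the contrast is (1-d')·(rp-rn). No effect gives 0. A true 5-point loss gives -4.75 to -4.25 at d' of 5-15%.

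Late seroconverters dilute this. If seroconversion is spread evenly over 52 weeks, only 16/52 of eventual positives are positive by Week 16. That is 0.20 × 16/52 = 6.2% to 0.30 × 16/52 = 9.2% of patients.
- a = 20%: later converters are (0.200 - 0.062)/0.938 = 14.8% of the negative group, so the contrast is -5 × 0.852 × 0.95 = -4.0 at d' = 5%.
- a = 30%: they are (0.300 - 0.092)/0.908 = 22.9%, so it is -5 × 0.771 × 0.85 = -3.3 at d' = 15%.

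**The case against.** The strongest reply is that the size rests on k, which the documents do not fix and partly argue against setting at 0.5. Patients who discontinue have an early termination visit and 12 weeks of follow-up (SAP 5.1.3, 5.1.4). The note to SAP Table AMAJ.6.2 combines the active-treatment and follow-up outputs for immunogenicity, so post-treatment samples may count. Patients stopped under the lack-of-benefit criterion have reached Week 24. The antibody sampling schedule is not in the documents supplied. All of this stands. At k = 0.8 the result is attenuation only.

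A reader might also infer that the SAP classes early leavers as antibody-negative. It does not say so. SAP 6.14.6 defers to compound-level safety standards that are not supplied, and these may contain an evaluability rule. What can be said is that 6.15.1 offers two categories and no stated place for an unevaluable patient.

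Nor is this the only planned look at the question. SAP 6.14.6 commits to further work in the integrated Phase 3 analysis, though without a method.

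The stakes are modest. The endpoint is exploratory and outside the multiplicity scheme. With 888 mirikizumab patients and 20-30% positive, an unbiased 70% vs 75% contrast has a standard error of 3.8 to 3.3 points and power of about 26-33%. The possible bias is of the same order as that standard error, and more patients would not remove it.

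**Conclusion.** The concern holds as a vulnerability, mainly at Week 52. Ever-positive status combined with NRI lets follow-up time influence both label and outcome. Under the assumed rates this attenuates a real loss of response. It hides or reverses one only if the loss is small (about 5 points) and dropouts are much less likely to be detected positive (k near 0.5, dropout of about 10% or more).

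The tempting stronger reading is that a real loss of efficacy will be hidden or reversed. The documents do not support it. They give no dropout rate, seroconversion rate or sampling schedule. A 10-point loss keeps its sign in every tabulated case and reverses only near the k = 0 bound. The direction is not fixed either: antibody-driven dropout makes the contrast larger than the on-treatment loss, although under the SAP's composite strategy some of that is legitimately counted as failure.

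An effect at Week 16 is not shown, since all the figures use dropout before Week 52. For the TE-ADA summaries, SAP 6.14.6 takes its postbaseline period from 6.14.2, which for the Induction Safety Population is the Induction Period. If the same limit applies to the Week 16 subgroup analysis, status there already uses induction samples only; 6.15.1 does not say. This is a cheap improvement to an exploratory analysis and does not touch the primary or major secondary conclusions.

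**What to change.** Keep the planned analysis and add the following to SAP 6.15.1, within the mirikizumab arms:

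- **Week 52 landmark.** Define TE-ADA status from samples up to Week 16 in patients still on treatment at Week 16, then compare Week 52 response by that status with NRI retained. Later dropout then cannot change the label, and antibody-related dropout after Week 16 still counts as nonresponse.
- **Week 16.** State that status for this comparison uses only samples up to Week 16.
- **Evaluability.** Report patients without an evaluable postbaseline antibody sample separately and not as negative, or cite the rule if the compound-level standards already contain one.
- **Discontinuation.** Tabulate treatment discontinuation by TE-ADA status, so that a reader can judge how far dropout drives the planned contrast.

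The cost is SAP wording, one derived variable and one table, with no new data. The downside is that patients who seroconvert after Week 16 count as negative in the landmark analysis, which means fewer positives and some dilution. With late seroconversion the positive group could be about 6-9% of mirikizumab patients, and might then fall below the 10% threshold in 6.15.1 and be summarised without testing. The landmark analysis also conditions on remaining on treatment to Week 16, a postbaseline event. For these reasons it should supplement the planned analysis and not replace it.

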5.1. Summary of Study Design

Study I6T-MC-AMAJ (AMAJ) is a Phase 3, multicenter, randomized, double-blind, placebo- and active-controlled, parallel-group, multi-period study in adult patients with moderate-to-severe plaque psoriasis. Approximately 1443 patients will be randomized to treatment groups involving different mirikizumab doses and regimens, placebo, or secukinumab. The study is comprised of 2 treatment periods (Induction and Maintenance), which together last for up to 52 weeks, followed by a 12-week Posttreatment Follow-Up Period.

5.1.1. Screening Period

Screening Period: Patients will be evaluated for study eligibility ≤ 28 days before the baseline visit (Visit 2). Electronic diary collection will begin at screening.

5.1.2. Baseline and Double-Blinded Induction Period (Week 0 to Week 16)

At Visit 2 (Week 0; baseline), patients who meet the study eligibility criteria will be randomly assigned to their induction and maintenance treatments with stratification based on previous exposure to biologic therapy (yes/no), body weight (<100 kg or ≥ 100 kg), and geographic region (North America, Europe, or Other). The treatment groups in the Blinded Induction Period are 250-mg mirikizumab or matching placebo (subcutaneous [SC]) administered at Weeks 0, 4, 8, and 12, and 300-mg secukinumab (SC) administered at Weeks 0, 1, 2, 3, 4, 8, and 12.

Patients who discontinue the study for any reason during this period will stop treatment and continue to the early termination visit (ETV) and then complete the 12-week Posttreatment Follow-Up Period.

5.1.3. Blinded Maintenance Period (Week 16 to Week 52 [36 Weeks])

Patients who were randomly assigned at baseline to receive mirikizumab in the Blinded Induction Period were also randomly assigned to receive either 250-mg mirikizumab every 8 weeks (Q8W) SC or 125-mg mirikizumab Q8W SC in the Blinded Maintenance Period, with maintenance dosing starting at Week 16 and ending at Week 48. Patients who were randomized to placebo in the Blinded Induction Period will receive 250-mg mirikizumab SC every 4 weeks (Q4W) for Weeks 16 through 32 and 250-mg mirikizumab Q8W thereafter. Patients who were randomized to 300-mg secukinumab SC in the Blinded Induction Period will continue this treatment with Q4W dosing during the Blinded Maintenance Period, starting at Week 16 and ending at Week 48.

Throughout the study, patients will receive placebo, as appropriate, to maintain the study blind across treatment groups.

A discontinuation criterion has been included for patients in any treatment group who remain at or above their baseline static Physician's Global Assessment (sPGA) score at Week 16 (Visit 9) and Week 24 (Visit 11), or remain at or above their baseline Psoriasis Area and Severity Index

(PASI) score at Week 16 (Visit 9) and Week 24 (Visit 11), to ensure patients who have not shown any benefit from study treatment are offered alternative therapies.

At Week 52, patients have 1 of the following options:

- Enter Study I6T-MC-AMAH (AMAH), a long-term extension study in which patients receive 250-mg mirikizumab Q8W SC or 125-mg mirikizumab Q8W SC, OR
- Discontinue study treatment and complete Study AMAJ's 12-week Posttreatment Follow-Up Period.

[figure not shown]
Patients who discontinue early from the study for any reason during this period will stop treatment and continue to the ETV and then the 12-week Posttreatment Follow-Up Period.

5.1.4. Posttreatment Follow-Up Period (12 Weeks)

Patients who do not enroll into Study AMAH or who discontinue early from Study AMAJ will complete the Posttreatment Follow-Up Period (Visit 801 and Visit 802) of Study AMAJ.

For patients who have entered the Posttreatment Follow-Up Period, psoriasis therapy with another agent(s), as determined appropriate by the investigator, is allowed.

[Figure AMAJ.5.1](#) illustrates the study design.

Abbreviations: LV = last study visit; miri = mirikizumab; Q4W = every 4 weeks; Q8W = every 8 weeks; SC = subcutaneous; V = visit; w = weeks; W = week.

* Option to enter Study I6T-MC-AMAJ or to enter the Posttreatment Follow-Up Period.

Note: At Week 0 (V2), patients will be randomized in a 4:4:4:1 ratio to one of the following induction and maintenance period treatments: a) 250-mg miri at Weeks 0, 4, 8, 12 followed by 250-mg miri SC Q8W starting at Week 16; b) 250-mg miri at Weeks 0, 4, 8, 12 followed by 125-mg miri Q8W starting at Week 16; c) 300-mg secukinumab at Weeks 0, 1, 2, 3, 4, followed by 300-mg secukinumab Q4W starting at Week 4; d) placebo at Weeks 0, 4, 8, 12, followed by 250-mg miri Q4W starting at Week 16 through Week 32 followed by Q8W thereafter. Patients will receive placebo to maintain the study blind across treatment groups as shown (patients receiving 125-mg miri will receive 1 placebo injection at weeks they receive miri and 2 placebo injections at other times shown). Dosing is via SC injection for all treatments in all periods.

Figure AMAJ.5.1. Illustration of study design for Clinical Protocol I6T-MC-AMAJ.

5.2. Determination of Sample Size

This section is based on the original AMAJ Protocol. The section was not changed in Protocol Amendment (b) due to the completion of the enrollment at the time of Amendment (b) approval.

Approximately 1443 patients will be randomized at a 4:4:4:1 ratio in the Blinded Induction Period to receive 250-mg mirikizumab SC at Weeks 0, 4, 8, and 12, then 250-mg mirikizumab SC Q8W, 250-mg mirikizumab SC at Weeks 0, 4, 8, and 12, then 125-mg mirikizumab SC Q8W, 300-mg secukinumab at Weeks 0, 1, 2, 3, and 4, followed by 300-mg secukinumab Q4W, or placebo. Stratified block randomization will be performed with the following stratification factors: previous exposure to biologic therapy (yes/no), body weight (<100 kg or \geq 100 kg), and geographic region (North America, Europe, or Other).

There are multiple primary endpoints in this study: the proportion of patients achieving a \geq 90% improvement in PASI from baseline (PASI 90) and the proportion of patients with a sPGA (0,1) with at least a 2-point improvement from baseline, comparisons between mirikizumab and placebo (test of superiority), and comparison between mirikizumab and secukinumab (test of non-inferiority). The assumed PASI 90 responses are 70% for the mirikizumab arm, 70% for the secukinumab arm, and 3% for the placebo arm. The assumed sPGA 0 or 1 responses are 70% for the mirikizumab arm, 70% for the secukinumab arm, and 5% for the placebo arm. Both PASI 90 and sPGA (0,1) rates at Week 52 are estimated to be 75% for both mirikizumab dose groups, and 65% for secukinumab group. The assumptions for mirikizumab are based upon the results of the mirikizumab Phase 2 Study I6T-MC-AMAF (Reich et al. 2017b) and review of historical clinical studies in psoriasis (Langley et al. 2014; Gordon et al. 2016; Blauvelt et al. 2017; Papp et al. 2017; Reich et al. 2017a). The assumptions for secukinumab were based upon 2 Phase 3 studies of secukinumab for psoriasis (Langley et al. 2014).

With 888 patients in the mirikizumab group and 111 patients in the placebo group, the estimated power is at least 99% to test superiority of mirikizumab to placebo on PASI 90 at Week 16, and on sPGA (0,1) at Week 16, respectively, at alpha of 0.05 two-sided. With 888 patients in the mirikizumab group and 444 patients in the secukinumab group, the estimated power is at least 90% to test noninferiority of mirikizumab to secukinumab at alpha of 0.025 one-sided with a noninferiority (NI) margin of 10% on PASI 90 at Week 16. Similarly, the estimated power is at least 90% to test noninferiority of mirikizumab to secukinumab at alpha of 0.025 one-sided with a NI margin of 10% on sPGA (0,1) at Week 16.

In addition, with 444 patients in the 250-mg mirikizumab Q8W group, 444 patients in 125-mg mirikizumab Q8W group, and 444 patients in the secukinumab group, the study will have an estimated power of 90% to test superiority of 250-mg mirikizumab Q8W compared to secukinumab at alpha of 0.05 two-sided on PASI 90 at Week 52, and sPGA (0,1) at Week 52, respectively, as well as 90% power to test superiority of 125-mg mirikizumab Q8W compared to secukinumab at alpha of 0.05 two-sided on PASI 90 at Week 52, and sPGA (0,1) at Week 52, respectively.

5.3. Method of Assignment to Treatment

Patients who meet all criteria for enrollment will be randomized to double-blind treatment at Week 0. Stratified block randomization will be implemented using a computer-generated sequence within an interactive web-response system (IWRS). The randomization will be stratified, based on previous exposure to biologic therapy (yes/no), body weight (<100 kg or ≥ 100 kg), and geographic region (North America, Europe, or Other). The IWRS will be used to assign prefilled syringes containing double-blind investigational product to each patient. Site personnel will confirm that they have located the correct carton(s) of pre-filled syringes by entering a confirmation number found on the carton(s) into the IWRS.

6. A Priori Statistical Methods

